7.7 NEUROLOGICAL ASSESSMENT

Neurological assessment will be performed by the Principal Investigator (or designee) at Screening Visit 1 (SV1), TE4, TE40, at least once within TE80-83 and TE116-123, and at Virologic Failure (VF) Visit.

The screening tool is based on the three question survey used by Simioni et al. [Simioni S, 2010]. Additional assessment modalities can be used for further assessment as per Investigator's discretion. Refer to [section 17.5](#) for further details.

7.8 QUALITY OF LIFE (QOL)

A quality of life assessment will be performed by the Principal Investigator or Study Coordinator at Screening Visit 1 (SV1), once every four weeks from TE4 through TE107, and at EOT. The instrument used for this assessment is the ACTG SF-21 (ACTG 601-602). Refer to [section 17.6](#) for further details.

7.9 VITAL SIGNS

The following vital signs will be collected:

- Height (at Screening Visit 1 only)

- Weight
- BMI (derived from the height and weight measurements; at Screening Visit 1 only)
- Seated blood pressure (taken after the subject has been seated for at least 5 minutes)
- Heart Rate
- Respiration Rate
- Temperature

Note: *Within Treatment Phase, post-treatment vital signs will be assessed within 15 minutes following study treatment administration..*

Note: *Vitals will not be collected when subjects perform self-administration.*

7.10 CLINICAL LABORATORY ASSESSMENTS

Blood samples will be collected according to the time points in the schedule of assessments for analysis of the following parameters:

7.10.1 Routine CBC

- Frequency of testing: Every 12 weeks from TE160 onwards, and at the end of Treatment Extension Phase OR at the time of virologic failure
- Includes hemoglobin, hematocrit (HCT), red blood cell (RBC) count, white blood cell (WBC) count, WBC differential count (%), absolute neutrophils count and platelets count.

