Name of Study Product: PRO 140 (Humanized monoclonal antibody to CCR5) Comparator: Historical Control	
Protocol Number: PRO 140_CD 01-Extension	Indication: Human Immunodeficiency Virus Type-1 (HIV-1) Infection
In addition to assessments scheduled at T12 for the PRO 140_CD 01 Treatment Substitution study, the following assessments will also be performed to determine eligibility for the PRO 140_Treatment Substitution Extension study:	

• Medical History• Physical Examination	
The lab results of blood samples collected at SV1 (or T12 of the PRO 140_CD 01 Treatment Substitution study) will be reviewed at SV2 (or T13 of the PRO 140_CD 01 Treatment Substitution study).	
Treatment Extension Phase (weekly ± 3 days):	
Treatment Extension (TE) Phase begins with an evaluation of results of laboratory samples collected during the Screening Phase. Subjects who meet all eligibility criteria, as per data gathered from Screening Phase are to be treated. All subjects who fail to meet eligibility criteria: 
• will be considered screen failures,• will not be allowed to enter the extension study,• will re-initiate their existing anti-retroviral therapy regimen at T13 visit under the existing PRO 140_CD 01 Treatment Substitution study, and• will proceed to enter follow-up phase after T14 visit depending on viral status.	
For subject who meets the eligibility criteria, the first Treatment Extension Visit (TE1) will take place 14 days from Screening Visit-1.	
Eligible subjects will receive weekly treatments, given every week (± 3 days) or until virologic failure, whichever occurs first. Treatment Extension Phase visits will commence on TE1, i.e. the date of first treatment, with weekly visits (± 3 days) thereafter.	
Efficacy assessments at each week will include assessment of viral load and CD4 cells count. Safety assessments will consist of physical exam, lab, and adverse event assessments at each Treatment Extension and Follow-Up Visits.	
The study treatment (PRO 140 SC injections) will be administered by a licensed medical professional (MD, DO, PA, LPN, LVN, NP, RN, or CMA if permitted by state law) or by subjects trained to perform self-administration of study treatment.	
All study subjects will re-initiate their previous antiretroviral regimen: 
• One week prior to the end of Treatment Extension Phase, or	

Name of Sponsor: CytoDyn Inc.	

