2 STUDY OBJECTIVES

The primary objective is to assess the long-term efficacy of PRO 140 monotherapy for the maintenance of viral suppression in patients who have completed 12 weeks of treatment under Protocol PRO 140_CD 01 without experiencing virologic failure.

The secondary objective of the trial is to assess the long-term clinical safety and tolerability parameters of continued PRO 140 use in patients who have completed 12 weeks of treatment under Protocol PRO 140_CD 01 without experiencing virologic failure.

The primary efficacy endpoint for this study is time to virologic failure after initiating PRO 140 monotherapy. Virologic failure is defined as two consecutive HIV-1 RNA levels of ≥ 400 copies/ml separated by at least 3 days.

The secondary efficacy endpoints will be proportion of participants with virologic failure after initiating PRO 140 monotherapy, mean change in viral load (HIV-1 RNA levels), mean change in CD4 cell count, and change in Quality of Life (QoL) up to TE107 within the treatment extension phase.

Safety assessments include evaluation of tolerability of repeated subcutaneous administration of PRO 140 as assessed by study participants (using Visual Analogue Scale) and by investigator – evaluation of injection site reactions, frequency of Grade 3 or 4 adverse events and frequency of Treatment-emergent serious adverse events.

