- [4] Medical history collected at the time of screening for PRO 140_CD 01 protocol will be carried forward. Medical history will not be collected for the PRO 140_CD 01-Extension protocol.
- [5] Symptom-directed physical examination
- [6] Performed by Principal Investigator or designated study personnel. The neurological assessment tool is based on the three question survey used by Simioni et al. (Simioni S, 2010). Additional neurological assessment modalities may be used as per Investigator's discretion.
- [7] Performed by Principal Investigator or Study Coordinator
- [8] Blood pressure, heart rate, respiration rate, temperature assessed before and 15 minutes after study treatment administered at clinic
- [9] Hemoglobin, Hematocrit (HCT), Red Blood Cells (RBC), White Blood Cells (WBC) with total and differential count, Absolute Neutrophil Count (ANC) and platelets.
- [10] Serum Biochemistry
 - Hepatic function indicators: total and direct bilirubin, alkaline phosphatase, aspartate aminotransferase (AST), alanine aminotransferase (ALT), total protein, Lactate dehydrogenase (LDH)
 - Renal function indicators: BUN, creatinine
 - Electrolytes: sodium, potassium, chloride, calcium and bicarbonate
 - Other: glucose (random), cholesterol (total)
- [11] ONLY performed on women of childbearing potential.
- [12] Includes: Absolute Lymphocytes, CD3 cell count, CD4 cell count, CD8 cell count, CD3 %, CD4 %, and CD8 %
- [13] PK samples for PRO 140 may be collected at during Treatment Extension Phase and at virologic failure
- [14] To assess subject compliance in abstaining from previous ART regimen after SV1 visit;
- [15] Blood sample collection prior to first treatment administration at SV2 and at the time of early breakthrough/virologic failure will be used for exploratory or confirmatory purposes.
- [16] ONLY for subjects trained to perform self-administration of study treatment on weeks when clinic visit optional, i.e., no lab samples are required
- [17] Study treatment for self-administration will be provided to subjects during treatment visits at clinic; used vials from prior self-administration must be collected and accounted for (see [Section 4.2.2](#))

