- [42] All study subjects will re-initiate their previous antiretroviral regimen: (1) One week prior to the end of Treatment Extension Phase, or (2) Anytime during the Treatment Extension Phase, if virologic failure occurs or have met any other criteria for discontinuation of study treatment as specified in the protocol.
- [43] As assessed by Investigator when study treatment administered at the clinic.
- [44] Subject-perceived injection site pain (average pain since last treatment) will be assessed using the Pain Visual Analog Scale (VAS) prior to each study treatment administration for subjects randomized to PRO 140.
- [45] Should be performed at least once every 12 weeks from TE160 onwards.

Table 4-9: Schedule of Assessments –Follow-Up (FU) Phase

(a) Subjects who do NOT experience virologic failure

Procedure/Assessments	Follow-Up Visit -1	Follow-Up Visit -2
	NVF-EFU1	NVF-EFU2
Window Period	2 weeks (±3 days) after TE161	4 weeks (±3 days) after TE161
Physical Examination	X ^[1]	X ^[1]
Vital Signs	X	X
Plasma HIV-1 RNA level	X	X
TruCount T assay	X	X
Previously used Antiretroviral Regimen	X	X
Adverse Events	X	X
Concomitant Medications	X	X
Anti-idiotypic Antibodies to PRO 140		X

[1] Symptom-directed physical examination

(b) Subjects who experience virologic failure

- Short term follow up visits

Procedure/Assessments	Follow-Up Visit -1	Follow-Up Visit -2	Follow-Up Visit -3 ^[1]
	VF-EFU1	VF-EFU2	VF-EFU3
Window Period	4 weeks (±7 days) after VF	8 weeks (±7 days) after VF	12 weeks (±7 days) after VF
Physical Examination	X ^[2]	X ^[2]	X ^[2]
Vital Signs	X	X	X
Plasma HIV-1 RNA level	X	X	X
TruCount T assay	X	X	X
Previously used Antiretroviral Regimen	X	X	X
Adverse Events	X	X	X
Concomitant Medications	X	X	X
Anti-idiotypic Antibodies to PRO 140	X		

[1] Subject will be followed up every 4 weeks until viral suppression is achieved (i.e., plasma HIV-1 RNA levels to return back to <50 copies/mL). Subject will undergo additional follow-up visits every 4 weeks beyond VF-EFU3 visit, if viral suppression is not achieved at the end of VF-EFU3 visit.

[2] Symptom-directed physical examination

(c) Subjects who experience virologic failure

- Long term follow up visits

Procedure/Assessments	Long-Term Follow-Up Visit -1	Long-Term Follow-Up Visit -2
	VF-12mFU	VF-24mFU
Window Period	12 months (± 1 month) after VF visit	24 months (± 1 month) after VF visit
Assessment of cART changes ^[1]	X	X
Plasma HIV-1 RNA level	X	X
TruCount T assay	X	X

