4.2.3 Treatment Visit-60 (TE60) onwards – Monthly Visits

Patients are required to have a clinic visit at least once every four weeks from TE60 onwards. Subjects will re-initiate previous antiretroviral regimen at end of treatment extension phase (one week prior to last PRO 140 treatment), if viral load remain suppressed.

The following assessments will be performed at every clinic visit:

- Assess for any Adverse Events and changes in Concomitant medications (see [section 9](#) and [7.5](#)),
- Symptom-directed physical examination (see [section 7.6](#)),
- Neurological Assessment (see [section 7.7](#))
- Vital Signs (see [section 7.9](#))
- **Note:** *Vitals not obtained when subject self-administers study treatment outside clinic*
- Study Treatment Administration (PRO 140)
- **Note:** *Subjects trained to perform self-administration of study treatment may self-administer when clinic visit not required (no lab sample collection needed)*

- Injection Site Reaction Assessment (see [section 7.12](#))
 - **Note:** *To assess injection site reactions, the investigator will use the DAIDS AE grading table (see [section 17.3](#)).*
 - **Note:** *Assessment will be performed when subject administered study treatment at clinic visit*
- Subject-perceived Injection Site Pain Assessment (see [section 7.13](#))
 - **Note:** *Subject-perceived injection site pain will be assessed using the Pain Visual Analog Scale (VAS) prior to study treatment administration assessing average pain at injection site since last treatment.*
 - **Note:** *Performed at the time of clinic visit.*
- Collection of Blood Specimens (see [section 7.10](#)) for
 - Plasma HIV-1 RNA level
 - TruCount T Assay
 - Routine CBC
 - Biochemistry
 - PK sample for PRO 140
 - Serum concentration of ART drugs
 - Anti-idiotypic antibodies to PRO 140
 - Blood sample for exploratory analysis
- **Note:** *Trofile® RNA or Trofile® DNA and PhenoSense Entry Assay will be performed at the last treatment visit (EOT)*
 - CCR5 Receptor Occupancy
- **Note:** *Blood will be taken prior to PRO 140 injection (trough sample) and 24-48 hours (peak sample) after the PRO 140 injection to check for CCR5 occupancy, and correlative analysis will be performed with PRO 140 PK concentration and HIV-1 RNA levels. This assessment will be performed up to 5 times at different treatment visits.*

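### Section 4.2.3 requires CBC and biochemistry at every clinic visit from TE60, while 7.10 and the schedule tables give none before TE160/TE161 and only 12-weekly panels after that

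*Protocol*

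**What the plan says.** Section 4.2.3 covers treatment visits from TE60. It states "Patients are required to have a clinic visit at least once every four weeks from TE60 onwards" and opens its list with "The following assessments will be performed at every clinic visit". Routine CBC and Biochemistry are both on that list. Notes restrict two other items, the tropism and entry assays (last treatment visit) and CCR5 occupancy (up to five times). No note restricts CBC or Biochemistry.

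Sections 7.10.1 and 7.10.2 give the frequency of each as "Every 12 weeks from TE160 onwards, and at the end of Treatment Extension Phase OR at the time of virologic failure". Section 7.10 ties sampling to the tables: "Blood samples will be collected according to the time points in the schedule of assessments". The tables show:

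- Tables 4-1 to 4-6 mark CBC and Biochemistry only in the virologic failure column.
- Table 4-7 marks them only at TE161 and at virologic failure.
- Table 4-8 marks them for weekly visits from TE160, at EOT and at virologic failure. Its footnote 45 on the weekly entry reads "Should be performed at least once every 12 weeks from TE160 onwards".

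The synopsis, under the Treatment Extension Phase, says "Safety assessments will consist of physical exam, lab, and adverse event assessments at each Treatment Extension and Follow-Up Visits". Section 2 states "The secondary objective of the trial is to assess the long-term clinical safety and tolerability parameters of continued PRO 140 use".

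**The concern.** A site cannot follow both rules. If 4.2.3 governs, the tables omit panels that the protocol requires. If 7.10 and the tables govern, as 7.10 suggests, a continuing subject receives weekly injections for about three years with no scheduled test of liver function, renal function, haemoglobin, neutrophils or platelets. Some subjects may move to 700 mg during that time. The TruCount assay does not fill the gap. Its footnote reads "Includes: Absolute Lymphocytes, CD3 cell count, CD4 cell count, CD8 cell count", followed by the corresponding percentages, so it reports lymphocytes and their subsets only.

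The safety results depend on these tests. Clinically significant laboratory abnormalities are to be recorded as adverse events (7.10.12, 9.1). Frequency of Grade 3 or 4 events is a safety endpoint (8.2.3). The DMC is to receive laboratory data (8.5.3), and laboratory values are to be summarised (8.7.5.3). A test that is not drawn contributes to none of these.

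**Working it through.** The protocol gives no panel count of its own, so the check counts scheduled CBC and biochemistry panels for a subject who neither fails nor stops early.

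**Inputs.** Clinic visits at least every 4 weeks from TE60 (4.2.3). Panels every 12 weeks from TE160 (7.10.1, 7.10.2, Table 4-8 footnote 45). Weekly visits counted from TE1 (4.2). Planned maximum of 28 subjects (synopsis). 23 of 43 CD01 subjects completed 12 weeks without virologic failure (1.5.2.7), which inclusion criterion 1 requires.

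**Counts, TE60 to TE156**

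- 4.2.3: (156 − 60)/4 + 1 = 25. Cross-check: Table 4-6 has 12 four-week blocks (TE60 to TE107), and TE108 to TE159 is 52/4 = 13 more; 12 + 13 = 25.
- 7.10 and the tables: 0.
- A 12-weekly rule from TE60: (156 − 60)/12 + 1 = 9.

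**Rate from TE160, per 52 weeks**

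- 4.2.3: 52/4 = 13.
- 7.10 and Table 4-8: 52/12 = 4.3.

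| Period | 4.2.3 | 7.10 and tables | 12-weekly from TE60 |
|---|---|---|---|
| TE60 to TE156 | 25 | 0 | 9 |
| From TE160, per 52 weeks | 13 | 4.3 | 4.3 |

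**Time from TE1 to the first scheduled panel**

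- Tables, at TE160: 159 × 7/365.25 = 3.05 years. At TE161: 160 × 7/365.25 = 3.07 years.
- If TE161 stops being a fixed visit and nothing else changes, footnote 45 alone would be satisfied by a first panel at about TE172: 171 × 7/365.25 = 3.28 years.
- 12-weekly from TE60: 59 × 7/365.25 = 1.13 years.

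**Can the text be read consistently?** The list in 4.2.3 points to 7.10 for blood specimens, which might be taken to import the 7.10 frequencies. Two features of the text go against that. The corresponding list in 4.2.2 carries an exception for anything specified elsewhere, and 4.2.3 drops it. Section 4.2.3 also writes out limits for the assays it means to restrict and gives none for these two. The conflict stands.

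**The case against.** The strongest reply is that the schedule governs, that it provides 12-weekly panels from TE160, and that the subjects concerned may already be past that point. The protocol refers to versions 1.0 to 9.0, describes CD01 in the past tense and cites guidance of March 2020. Few or no subjects may still be in the TE60 to TE156 window. This limits the size of the gap from now on, but the protocol gives no numbers, and the 4-weekly against 12-weekly conflict persists after TE160.

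The earlier safety record is also reassuring. Primate dosing for 24 weeks did not change haematology or chemistry, no pattern of drug-related toxicity was seen in the completed trials, and CD03 is running 48 weeks at up to 700 mg. That is fair context. However, CD03 is listed as ongoing, and the longest completed schedule in Table 1-1 is 25 weeks, at 350 mg.

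Three stronger readings are tempting, and the document does not support them.

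- A reader might take the synopsis as demanding CBC and chemistry at every visit. Its word for laboratory tests is generic and could cover viral load, TruCount, PK or antibody samples, so the point rests on 4.2.3 against 7.10.
- A reader might infer from the antiretroviral marks at TE160 and TE161 in Table 4-7 that sites would restart ART in subjects meant to continue on monotherapy. Footnote 43 to that row, like footnote 42 in Table 4-8, ties the restart to one week before the end of the Treatment Extension Phase without fixing its length. Section 7.5.1 allows ART only for the closing one-week overlap, or after failure or discontinuation. The remaining 161-week wording is an editorial leftover.
- A reader might infer that safety is unmonitored. Adverse event reporting, vital signs, examinations and unscheduled tests remain, and a subject who stops early for a reason other than virologic failure has the TE161 assessments, which include both panels.

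**Conclusion.** The conflict is real, sits in current operative text and should be corrected. In a subject who neither fails nor stops, the two rules differ by 25 panels to 0 over TE60 to TE156, and threefold from TE160. If the tables are followed, the first scheduled panel comes about 3.05 years after TE1. The counts assume 4-weekly clinic visits, which is the minimum 4.2.3 allows, and a subject who remains on treatment throughout. For TE1 to TE59, 4.2.2 and the tables agree in scheduling no panel, so the contradiction starts at TE60, although the 3.05 years includes that first stretch.

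The consequence is for the laboratory part of the secondary, safety objective. The primary endpoint and its analysis do not depend on these tests.

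**What to change.** State one frequency in 4.2.3, 7.10.1, 7.10.2 and Tables 4-6 to 4-8: CBC and biochemistry at least every 12 weeks from TE60, plus EOT and virologic failure, at clinic visits where blood is already drawn. Subjects already past TE60 start at the next clinic visit. The interval is a choice: it brings forward the one the protocol already uses from TE160. If the sponsor intends the 4-weekly rule of 4.2.3, the tables should say so.

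Cost relative to the tables: at most 9 extra panels per continuing subject before TE160, which is 25 − 9 = 16 fewer than 4.2.3 asks for. That is 23 × 9 = 207 panels if all 23 CD01 completers continued, and at most 28 × 9 = 252 for the planned maximum. There is no extra visit or venepuncture, and nothing is added to the 12-weekly rule from TE160.

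Editorial corrections for the same amendment:

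- Replace the 161-week and TE161 wording with EOT in the two notes of 4.2, footnotes 18 and 29, and the follow-up anchor of Table 4-9(a).
- Keep the last two treatment columns of Table 4-7, but relabel TE160 as EOT minus 1 week, retaining the ART restart, and TE161 as EOT. Deleting them would remove the only table entry for the restart one week before the end, and the only end-of-treatment quality-of-life mark outside the virologic failure column.
- Mark quality of life at EOT, as 7.8 requires.
- Align the weekly viral-load wording in the synopsis with 7.10.6, which measures every 2 weeks to TE58 and at least every 4 weeks beyond TE60.

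Make the relabelling and the laboratory change together. Relabelling alone would remove TE161 as a fixed sampling point and let the first panel slip to about TE172.

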7.10.2 Biochemistry

- Frequency of testing: Every 12 weeks from TE160 onwards, and at the end of Treatment Extension Phase OR at the time of virologic failure
- Biochemistry profile includes assessment of
 - Hepatic function indicators: total and direct bilirubin, alkaline phosphatase, aspartate aminotransferase (AST), alanine aminotransferase (ALT), total protein, LDH
 - Renal function indicators: BUN, creatinine
 - Electrolytes: sodium, potassium, chloride, calcium and bicarbonate
 - Other: glucose (random), cholesterol (total)

7.10.3 PK sample for PRO 140

- Frequency of testing: At first Screening Visit, at Treatment Visits 4, 8, 12, 16, 20, 24, 28, 32, 36, 40, 44, 48, 52 and 56. Beyond TE60, PK sample for PRO 140 assessment will be performed once every four weeks, and at Virologic Failure (VF) Visit.

7.10.4 Serum pregnancy test

- Frequency of testing: At first Screening Visit
- Only for female subjects of childbearing potential. Childbearing potential is defined as someone who is not surgically sterile or is not more than one year past complete cessation of menstrual cycles.

7.10.5 Urine pregnancy test

- Frequency of testing: At second Screening Visit prior to first treatment administration
- A urine sample will be collected from female subjects of childbearing potential. This test will be performed at the study site using a commercially available kit.

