Name of Study Product: PRO 140 (Humanized monoclonal antibody to CCR5) Comparator: Historical Control	
Protocol Number: PRO 140_CD 01-Extension	Indication: Human Immunodeficiency Virus Type-1 (HIV-1) Infection

 During the Treatment Extension Phase, if virologic failure occurs or have met any other criteria for discontinuation of study treatment as specified in section 5.2 of the PRO 140_Treatment Substitution Extension Study protocol. 
Subjects who experience virologic failure (defined as two consecutive HIV-1 RNA levels of ≥ 400 copies/ml separated by at least 3 days) at any time during the Treatment Extension Phase will undergo the Virologic Failure (VF) Visit assessments and then exit the Treatment Extension Phase to enter the Follow-up Phase of the study.
 
Subjects who do not experience virologic failure will enter the Follow-up Phase of the study at the end of Treatment Extension Phase.
	

Follow-up Phase:
 
Duration of Follow-up Phase is determined based on whether or not subject has experienced virologic failure during the Treatment Extension Phase.
 
 Subjects who experience virologic failure will be followed up every 4 weeks until the viral suppression is achieved (i.e., plasma HIV-1 RNA levels return to <50 copies/mL) Subjects who do not experience virologic failure at the end of Treatment Extension Phase, will be followed up every 2 weeks for total of 4 weeks. 
➤ Note: Virologic failure subjects will have a long term safety follow up visit once a year within 2 years of completing the last VF-FU visit.
	

Duration of Study:
 
 Screening Phase: 14 ± 3 days Treatment Extension Phase: Weekly \pm allowed windows (± 3 days). Follow-up Phase: 
 Virologic Failure: Until viral suppression is achieved Non-Virologic Failure (NVF): 4 weeks 
Total Study Duration:
 
Weekly until IP receives marketing approval or IND is withdrawn by Sponsor. [Does not include additional follow-up time for virologic failure subjects]
	

Inclusion Criteria: Potential subjects are required to meet all of the following criteria for enrollment into the study.
 
 Subjects who have completed 12 weeks of treatment in PRO 140_CD 01 study without experiencing virologic failure. 	

Name of Sponsor: CytoDyn Inc.	

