1.7.1.4 Pregnancy

Risks to unborn babies are unknown at this time; pregnant females will be excluded from this study. Females of childbearing potential must have a negative pregnancy test prior to enrollment. Both male and female patients and their partners of childbearing potential must agree to use appropriate birth control methods throughout the study duration (excluding women who are not of childbearing potential and men who have been sterilized).

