5.2 SUBJECT WITHDRAWAL

A subject who enters the Treatment Extension Phase but does not complete the study, as defined in [Section 5.1](#), is considered to have prematurely withdrawn from the Study.

All subjects have the right to withdraw at any point during treatment without prejudice to future care. It will be documented whether or not each subject completed the clinical study. If for any subject, study treatment or observations were discontinued, the reason(s) will be recorded.

The Investigator can discontinue a subject at any time if it is considered medically necessary.

In addition, subjects WILL be withdrawn from the study, in consultation with the Medical Monitor and the Investigator, if any of the following are met:

- A subject is significantly non-compliant with the requirements of the protocol.
- The investigator determines that it is in the best interest of the subject.
- Subject chooses to withdraw or is withdrawn due to an adverse event
- A subject becomes pregnant

Note: *The pregnancy will be followed to term for safety follow-up. Relevant safety information collected after the study has completed will be reported as supplemental information.*

- Discontinuation of study by Sponsor

Premature withdrawal from the study MAY occur if, in consultation with the Medical Monitor and the Investigator, any of the following are met:

- A subject is treated with a prohibited medication.
- Major protocol violation

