5.2.1 Discontinuation of Study Treatment

Discontinuation of study treatment and resumption of previous antiretroviral therapy is recommended if:

- Subject experiences virologic failure (defined as two consecutive HIV-1 RNA levels of ≥ 400 copies/ml separated by at least 3 days)
- Develops retroviral rebound syndrome or AIDS-defining conditions as specified in Appendix I ([Section 17.1](#)).
- Shows signs or symptoms of clinically significant immunosuppression
- Subject or the subject's clinician wishes to restart ART.
- Subject becomes pregnant.

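### No pregnancy test is scheduled after the second Screening Visit, although weekly dosing is open-ended and fetal risk is stated as unknown (minor safety point; 0 to 3 women)

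*Protocol*

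**What the plan says.** Pregnancy testing is confined to screening and to women of childbearing potential. Protocol 7.10.4 gives the serum test as "Frequency of testing: At first Screening Visit". Protocol 7.10.5 places the urine test "At second Screening Visit prior to first treatment administration". Section 4.1.1 and Table 4-1 agree.

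The protocol treats pregnancy as serious. Section 1.7.1.4 states: "Risks to unborn babies are unknown at this time; pregnant females will be excluded from this study". Section 5.2 says that "subjects WILL be withdrawn from the study, in consultation with the Medical Monitor and the Investigator, if any of the following are met", and the list under it includes "A subject becomes pregnant". Section 5.2.1 opens with "Discontinuation of study treatment and resumption of previous antiretroviral therapy is recommended if" and lists "Subject becomes pregnant".

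The synopsis gives the study duration as "Weekly until IP receives marketing approval or IND is withdrawn by Sponsor". Section 4.2 lets subjects enrolled under earlier protocol versions move from 350 mg to 700 mg weekly. From TE60, 4.2.3 requires a clinic visit at least every four weeks, with self-administration possible in between.

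**The concern.** Two sections make a subject's continued treatment depend on whether she is pregnant, but after screening the schedule contains nothing that would establish it. If contraception fails and the subject does not recognise the pregnancy, weekly PRO 140 can continue with no scheduled event to bring 5.2 or 5.2.1 into play.

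Two things are at stake: the length of fetal exposure to a product whose fetal risk is unknown, and the delay before the woman returns from investigational monotherapy to her previous antiretroviral regimen, as 5.2.1 recommends. Doubling the dose without a test adds to the first.

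**Working it through.** There is no planned figure to reproduce. The check is a search of the schedule, a count of who can be affected, and the arithmetic of the remedy.

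**1. Scheduled tests**
- Table 4-1: the pregnancy rows are marked only at SV1 (serum) and SV2 (urine).
- Tables 4-2 to 4-5: the rows are present but empty, including the VF column.
- Tables 4-6 to 4-9: there is no pregnancy row.
- Visit lists in 4.2.1 to 4.2.4 and 4.3.1: no pregnancy test is named.
- Section 4.2, dose increase: no test is tied to it.

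Count: 2 tests in screening and 0 from TE1 onwards. The text and the tables agree, so this is not a table-reading artefact.

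**2. Last test to first extension dose.** TE1 is 14 days from SV1 (synopsis), and SV2 is nominally 7 days after SV1 (section 4). The gap is 14 − 7 = 7 days, before visit windows.

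**3. Length of untested dosing.** It is open-ended by the synopsis. The numbered schedule alone runs to 161 weekly visits.

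**4. Reach**
- Entry requires CD 01 enrolment (3.3.2) and 12 weeks there without virologic failure (3.3.1).
- CD 01 enrolled 40 men and 3 women, with median age 55 years and range 26 to 72 for all subjects (1.5.2.7). The ceiling is therefore 3 women.
- Of the 43, 23 completed 12 weeks without virologic failure. If failure were unrelated to sex (an assumption), about 3 × 23/43 = 1.6 women would have qualified, before considering childbearing potential.
- The women's ages and childbearing potential are not stated. The range is 0 to 3.

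**5. Existing safeguards**
- Contraception throughout (3.3.1) lowers the risk but does not detect a pregnancy.
- Adverse-event questioning (9.1), prompt reporting of events between visits (Table 4-7, note 34), symptom-directed examination (4.2.2, 4.2.3) and medication questioning at each visit (7.5) may raise suspicion and prompt an unscheduled test. A stopped birth-control pill, for example, could come to light this way.
- Reporting, follow-up to birth and registry entry (9.2) act once a pregnancy is known.
- Under 7.14, dosing may continue when clinic visits are missed. The weekly call covers compliance, adverse events and medication changes. Pregnancy is not listed.

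**6. Size of the remedy**
- TE60 to TE160 at every fourth visit: (160 − 60)/4 + 1 = 26 tests per subject, so at most 3 × 26 = 78 kits.
- After TE160: 52/4 = 13 per subject-year, so at most 3 × 13 = 39 kits a year.
- Weekly doses between tests: 4 if every visit is attended, 8 after one missed visit, 12 after two. Four weeks is a scheduled interval and not a guaranteed limit on exposure.

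**The case against.** The strongest case against has four parts.

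- **Nothing in the protocol is wrong on its own terms.** A negative test is required before enrolment or first dose, and the schedule delivers it. Sections 5.2 and 5.2.1 say what follows if a subject becomes pregnant, without promising periodic screening. This stands. A reader might infer that the protocol contradicts itself or breaks its entry rule, and the documents do not support that.
- **Perhaps nobody is affected.** The cohort is closed and small, its median age is 55, and the women may have failed treatment or left. This also stands, and it keeps the point minor. A reader might infer that women are known to be at risk; the documents show only that up to 3 could be.
- **Safeguards exist.** It would be too strong to say that they could never bring a pregnancy to light. What remains is that all of them depend on the subject or the site noticing something.
- **Some added tests would achieve little.** No PRO 140 is given at the VF visit and antiretroviral therapy restarts there, so a test at VF averts no dose. A test before the EOT dose averts at most that one. Both points stand. The protocol also does not establish four weeks as the right frequency; it is chosen because those visits already take place. Section 7.10 uses 12 weeks for blood count and biochemistry from TE160, but a urine test at a visit already attended costs little enough to justify the shorter interval.

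**Conclusion.** The point holds as a minor weakness in safety design, worth considering in the next amendment. If the plan is followed exactly, an unrecognised pregnancy meets no scheduled check during open-ended weekly dosing or before a doubling of the dose. The reach is 0 to 3 women and may be zero.

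A reader might also look for an effect on the trial's conclusions. There is none: the primary endpoint and the planned analyses do not depend on pregnancy testing.

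The conclusion rests on the assessment schedule, which is a protocol matter and is fully shown, and on the assumption that at least one woman of childbearing potential may still be on treatment. The documents neither confirm nor exclude that. The withdrawal rule in 5.2 operates in consultation with the Medical Monitor and the Investigator, and 5.2.1 is a recommendation; the finding does not require either to be absolute.

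**What to change.** Amend 7.10.5, 4.2.3 and Tables 4-6 to 4-8 so that any subject of childbearing potential still on treatment repeats the urine kit test, before dosing, at these points:

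- the clinic visits already held at least every 4 weeks from TE60;
- before any increase to 700 mg;
- clinic visits before TE60, only if a subject is still in that period (then also 4.2.2 and Tables 4-1 to 4-5).

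State that a positive result triggers 5.2 and 5.2.1. A test before the EOT dose is optional. None is needed at VF for limiting exposure.

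Add a pregnancy question to the weekly call in 7.14. It will not reveal a pregnancy that the subject has not recognised, but it prompts disclosure and testing on suspicion. If a clinic visit is missed, test at the next attended visit and do not stop home dosing, so that monotherapy is not interrupted for want of a test.

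The cost is amendment wording, one question in an existing call, and a kit already specified: at most 26 tests per subject from TE60 to TE160, then 13 per subject-year, plus one before a dose increase. Subjects' current visits are not stated, so the real number may be lower. The downside is a minor burden for at most 3 subjects; if no such subject remains, only the wording changes.
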